6.3.4. Baseline

For efficacy evaluations, the last adequate assessment on or before the date of randomization will be used as the baseline. Per protocol, the first QoL assessment is planned to occur on Cycle 1 Day 1 before the start of study treatment. Therefore, for QoL assessments only, if there is no value available on or before the date of randomization, then the last measurement on or before the start of study treatment will be used as the baseline.

For summaries of baseline characteristics based on the FAS, baseline will be defined as follows:

- For subjects randomized and not dosed: the last assessment on or before the date of randomization
- For subjects randomized and dosed: the last assessment on or before the start of study treatment

For safety evaluations, the last assessment on or before the start of study treatment will be used as the baseline.

If, per protocol, an assessment is to be performed on study day 1, before the first dose of study treatment, and the assessment time, time of first dose of study treatment, or both, is missing (or not collected), it will be assumed that the assessment is performed before study treatment administration. Unscheduled assessments will be used in the determination of baseline; however, an unscheduled assessment on study day 1 will be considered to have been obtained after study treatment administration.

If no assessment meets the definition of baseline for an evaluation, the baseline will be set to missing.

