- 18 Coagulation: activated partial thromboplastin time (aPTT) at baseline and international normalized ratio (INR). Blood for coagulation studies is to be obtained at Screening, on Day 1 (\pm 3 days) of each treatment cycle, and at the EOT Visit.
- 19 LVEF assessment required within 4 weeks prior to C1D1 (Week 1). ECHO/MUGA should be performed at other times during the study if clinically indicated; if repeated, method (per institutional policy) should be the same throughout the study for the individual subject. Only ECHO may be used at sites in Germany.
- 20 Safety ECGs; not central or triplicate. To be obtained at Screening, 4-6 hours post-dose on C1D1 (Week 1) only, and during the visit window on C1D15 (Week 3), C2D1 (Week 5), and C2D15 (Week 7). After Cycle 2, ECGs should be performed on D1 of each cycle and as clinically indicated. An ECG will also be performed at EOT.
- 21 Quality of life assessments will occur prior to dosing on Days 1 and 15 (\pm 3 days) of the first 2 cycles (Weeks 1 and 3 and Weeks 5 and 7); Day 1 (\pm 7 days) of odd cycles (Weeks 9, 17, 25, etc.); at EOT; and 4 weeks post-treatment. Upon Sponsor unblinding, quality of life assessments will not be conducted.
- 22 AG-120/placebo is administered QD beginning on C1D1 (Week 1), prior to administration of azacitidine. If subjects forget to take the daily dose, they should take AG-120 or placebo within 12 hours after the missed dose. Missed doses outside this window or vomited doses should not be taken or repeated.
- 23 Azacitidine will be administered SC or IV for 1 week (7 days) of each 4-week (28-day) treatment cycle, starting on Day 1 (\pm 3 days) of Week 1. A full 7 days of azacitidine is required, but as per institutional practice, a schedule of 5 days of daily doses, followed by no dose received on the weekend and 2 daily doses given again at the start of the next week, is allowed. The same schedule should be used for each subject throughout the duration of treatment, when possible.

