6.3.2. Start and End Dates of Study Drug and Study Treatment

The **start of study drug** (AG-120 or matched placebo or azacitidine) is the earliest date of administration of a non-zero dose of the study drug.

The **end of study drug** (AG-120 or matched placebo or azacitidine) is the latest date of administration of a non-zero dose of the study drug on or before the data cutoff date.

The **start of study treatment** is the earliest of the non-missing start of any study drug.

The **end of study treatment** is the latest of the non-missing end of any study drug.

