6.3.5. On-Treatment Period

The on-treatment period starts on the date of the start of study treatment and ends 28 days after the end of study treatment.

Data listings will include all assessments and events, with those that occur outside of the on-treatment period flagged.

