- Frequency of subjects with notable ECG values, defined as those in the following categories:
 - QT/QTc interval increase from baseline >30 ms, >60 ms
 - QT/QTc interval >450 ms, >480 ms, >500 ms

All ECG assessments and qualitative ECG abnormalities will be presented in by-subject listings.

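### SAP 6.3.4, applied by date as written, makes the post-dose Cycle 1 Day 1 ECG the QTc baseline, which would pull the >30 ms and >60 ms increase counts toward no difference between arms

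*SAP*

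**What the plan says.** **Baseline rule.** SAP 6.3.4 states: "For safety evaluations, the last assessment on or before the start of study treatment will be used as the baseline".

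**Start of treatment.** SAP 6.3.2 says the start of each study drug "is the earliest date of administration of a non-zero dose of the study drug", and the start of study treatment "is the earliest of the non-missing start of any study drug". Both are dates with no clock time.

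**Day 1 rules.** SAP 6.3.4 adds two. The first opens "If, per protocol, an assessment is to be performed on study day 1, before the first dose of study treatment" and, where the assessment time or the dose time is missing, says "it will be assumed that the assessment is performed before study treatment administration". The second treats an unscheduled Day 1 assessment as post-dose.

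**ECG schedule.** Protocol Table 6, footnote 20: "To be obtained at Screening, 4-6 hours post-dose on C1D1 (Week 1) only". Protocol 10.6.4 gives the same timing. No pre-dose ECG is planned on C1D1.

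**Use of the baseline.** SAP 6.3.5: "The on-treatment period starts on the date of the start of study treatment". SAP 7.8.5 draws on all on-treatment ECGs and counts subjects with "QT/QTc interval increase from baseline >30 ms, >60 ms". It also counts subjects above 450, 480 and 500 ms. Baseline ECGs supply the QT-RR and QTc-RR correlations and, if it is needed, the QTcP regression slope.

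**The concern.** A baseline for a drug with a QT signal should be free of the drug. Protocol 9.9.1 names QT prolongation as an expected risk of AG-120, and the C1D1 ECG is timed to follow the first dose. If that ECG serves as baseline, whatever the first dose does to QTc is subtracted from every later AG-120 value. Placebo values carry no AG-120 effect to subtract.

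At stake are the >30 ms and >60 ms increase counts, the only change-from-baseline QTc summaries that SAP 7.8.5 lists.

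**Working it through.** The plan states no figure for this point, so there is nothing to reproduce. The check is mainly one of text.

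**1. Which ECG does the rule select?** Two ECGs are planned up to and including the treatment start date: Screening (before it) and C1D1 at 4-6 hours post-dose (on it). Compared by date, both qualify and C1D1 is the later, so C1D1 is selected. A recorded clock time does not alter this, because the comparator defined in 6.3.2 has none.

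**2. Does a Day 1 rule exclude it?**
- The missing-time rule covers assessments the protocol plans before the first dose. This ECG is planned after it, so the rule does not apply.
- The deemed-post-dose rule covers unscheduled assessments. This ECG is scheduled, so the rule does not apply.
- SAP 7.8.5 sets no ECG-specific baseline.

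**3. What follows?** Let S, D and L be the QTc at Screening, at C1D1 post-dose and at a later visit.
- Screening as baseline: the C1D1 change is D − S and the later change is L − S.
- C1D1 as baseline: the C1D1 change is D − D = 0 and the later change is L − D = (L − S) − (D − S).

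The C1D1 ECG can then never register an increase, and later changes shrink by D − S, which in the AG-120 arm includes any first-dose effect. The absolute categories use L alone and do not move.

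**4. Illustration of size (all effect inputs assumed).** Protocol 5.2.3.1 reports about 1.7-fold Cmax accumulation at 500 mg once daily. Suppose that the QTc effect is proportional to concentration, that the C1D1 ECG falls at the first-dose peak, and that later ECGs fall at the steady-state peak. The share f of the steady-state effect already in the baseline is then 1/1.7 = 0.588, or 59%. A smaller share, f = 30%, is shown for range.

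With true mean rise m and normal changes, the observed mean is m(1 − f), and P(change > c) = 1 − Φ((c − m(1 − f))/SD). With SD 20 ms assumed:

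| True mean rise | Measure | Screening baseline | f = 30% | f = 59% |
|---|---|---|---|---|
| 10 ms | observed mean | 10 ms | 7.0 ms | 4.1 ms |
| | P(>30 ms) | 15.9% | 12.5% | 9.8% |
| | P(>60 ms) | 0.6% | 0.4% | 0.3% |
| 20 ms | observed mean | 20 ms | 14.0 ms | 8.2 ms |
| | P(>30 ms) | 30.9% | 21.2% | 13.8% |
| | P(>60 ms) | 2.3% | 1.1% | 0.5% |
| 30 ms | observed mean | 30 ms | 21.0 ms | 12.4 ms |
| | P(>30 ms) | 50.0% | 32.6% | 18.9% |
| | P(>60 ms) | 6.7% | 2.6% | 0.9% |

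With SD 15 ms and a 20 ms rise, P(>30 ms) is 25.2%, 14.3% and 7.3% across the three columns. These are probabilities for a single later ECG. The SAP counts subjects over all on-treatment ECGs, so they are not the planned statistic.

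**The case against.** The best counter-argument is that 6.3.4, read whole, already intends a pre-dose baseline. A rule for missing clock times is needed only if clock times decide Day 1 eligibility. A rule that treats unscheduled Day 1 values as post-dose has effect only if post-dose values cannot be baseline. The section also places the first QoL assessment on C1D1 before the start of study treatment, which uses that start as a moment within the day. On this reading the Screening ECG is the baseline and nothing is biased.

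This stands as evidence of intent, and a careful programmer might infer it. It does not remove the gap. The definition in 6.3.2 is a date, and the authors wrote an exclusion for unscheduled Day 1 values but none for scheduled post-dose ones.

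Other limits also stand:
- Membership of both periods is not a fault peculiar to this ECG. Under 6.3.5 every Day 1 value, pre-dose laboratory results included, falls in the on-treatment period. What is particular here is that the value is drug-exposed.
- QTcP is used only if QTcB and QTcF correct poorly, and no slope bias has been shown.
- Either arm may receive QT-prolonging antiemetics (Protocol 9.13.2 and 9.13.4), so a placebo C1D1 ECG need not be free of every drug effect. The difference between arms concerns AG-120 alone.
- Later ECGs are not timed to peak, so 59% is an upper illustration.

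A reader might also infer that AESI reporting of QT prolongation is biased. The documents do not support that. SAP 7.8.1.1 identifies AESIs by adverse-event search criteria. Expedited reporting under Protocol 11.2.3.1 rests on the event as graded, mainly on absolute QTcF above 500 ms. Its one change-from-baseline element requires an accompanying serious arrhythmia or its signs or symptoms, and does not call on the SAP derivation.

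**Conclusion.** The rule is wrong as written at date level. Applied literally, it selects a post-dose ECG as the QTc baseline. It would be too strong to say that QTc increases on AG-120 will be understated: that depends on a date-only derivation, and the Day 1 rules point the other way.

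If the rule is applied by date, two consequences need no assumed effect size. The C1D1 ECG has a change of exactly 0, and the baseline QT-RR and QTc-RR correlations use drug-exposed ECGs. The pull of the >30 ms and >60 ms counts toward no difference assumes only that AG-120 has raised QTc by 4-6 hours after the first dose.

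The size of that pull cannot be derived, because the documents give neither a QTc effect in ms nor an SD. The tabulated figures rest on assumed values, and the 59% share is a worst case. The absolute QTc categories, AESI reporting, and the primary and key secondary analyses are unaffected. Severity is low to moderate.

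**What to change.** Add to SAP 6.3.4:

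> For ECG, baseline is the last ECG obtained before the first dose of any study drug (normally Screening); the protocol-scheduled C1D1 4-6 hour post-dose ECG is an on-treatment assessment and is never baseline.

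With only the planned ECGs, the baseline is then the Screening ECG and contains none of the AG-120 effect. The cost is one sentence and a matching line in the ECG derivation. The protocol already requires a Screening ECG for every subject, so no new data are needed. If the sponsor already intends this, the sentence simply records it.

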6.3.5. On-Treatment Period

The on-treatment period starts on the date of the start of study treatment and ends 28 days after the end of study treatment.

Data listings will include all assessments and events, with those that occur outside of the on-treatment period flagged.

6.3.6. Start of Subsequent Anticancer Therapy

The start of subsequent anticancer therapy is used in censoring for efficacy analyses. The earliest start date, on or after randomization, captured in the Anticancer Therapy eCRF page will be used in the analyses as the start of subsequent anticancer therapy. If the option “HSCT Conditioning” is selected, the corresponding date will not be used in the derivation of start of subsequent anticancer therapy.

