- 12 A bone marrow aspirate (and biopsy if standard of care, or in case of a dry tap or aspirate [diluted] sample) is required at: Screening (if a sample was collected and submitted as part of Pre-screening within 28 days prior to randomization, an additional Screening sample is not required); Day 1 (± 7 days) of Weeks 9, 17, 25, 33, 41, 53, and every 24 weeks thereafter; at EOT; during EFS follow-up (samples should continue being collected during EFS according to the same schedule that was used when the subject had the EFS event; bone marrow samples are optional during EFS follow-up for post-transplant subjects); as dictated by physical exam and/or blood counts; and/or any time that disease progression is suspected. At EOT, a bone marrow aspirate will be collected if it has not been collected within the prior 8 weeks. Upon Sponsor unblinding, bone marrow aspirate will no longer be collected.
[REDACTED] Blood draws for regular hematology assessments and associated CBC results (footnote 17) should be reviewed for the need to evaluate disease status at an unscheduled time point.
- 13 Peripheral blood for IDH-mutated cells/leukemic blasts is required to be sampled at any time a bone marrow aspirate/biopsy is performed to assess for potential clinical activity. These time points include: Screening (if a sample was collected and submitted as part of Pre-screening within 28 days prior to randomization, an additional Screening sample is not required); Day 1 (± 7 days) of Weeks 9, 17, 25, 33, 41, 53, and every 24 weeks thereafter; at EOT; during EFS follow-up on the same schedule; as clinically indicated; and/or any time that disease progression is suspected.
[REDACTED] Blood draws for regular hematology assessments and associated CBC results (footnote 17) should be

- reviewed for the need to evaluate disease status at an unscheduled time point.

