12.5.1. Analyses of the Primary Endpoint

The analysis for the primary endpoint will be performed at the time when 173 EFS events have occurred. Event-free survival is defined as the time from randomization until treatment failure, relapse from remission, or death from any cause, whichever occurs first. Treatment failure is defined as failure to achieve CR by Week 24. Subjects who do not achieve CR by Week 24 will be considered to have had an event at Day 1 of randomization. For the remaining CR responders, the event time will be the time of either disease relapse or death, whichever occurs first. Event-free survival will be censored upon initiation of a new anticancer therapy should a new therapy be initiated prior to any EFS event.

Event-free survival will be tested using the log-rank test stratified by the randomization stratification factors (de novo status and geographic region) based on the data in the ITT Analysis Set. The basis for a claim of efficacy will be the statistical significance of EFS in favor of the AG-120 + azacitidine arm when the 1-sided $p \leq 0.025$ (observed EFS HR ≤ 0.742).

The distribution of EFS will be estimated using the KM method. The KM curves and 25th, 50th (median), and 75th percentiles (if estimable), along with their 2-sided 95% CIs, will be presented for each treatment arm. The KM estimates at individual time points (eg, 3-, 6-, and 12-month rates) will also be presented for each treatment arm. A Cox regression model stratified by randomization stratification factors will also be used to estimate the HR of EFS. However, given that the assumption of proportional hazards is not met based on the EFS definition, the overall HR is less meaningful in this context. As EFS is a composite endpoint, the estimates presented separately by each component are more meaningful: CR rate by 24 weeks and EFS among those who have achieved CR by 24 weeks. For subjects who achieve CR by 24 weeks, the KM curves

of the EFS distribution and 25th, 50th (median), and 75th percentiles (if estimable) along with their 2-sided 95% CIs will be presented for each treatment arm. A Cox regression model stratified by randomization stratification factors will also be used to estimate the HR of EFS for these subjects. In addition, the ratio of restricted mean survival time, which does not rely on proportional hazards assumptions, between the 2 arms will also be presented to summarize the treatment effect.

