7.6.1. Subsequent Stem Cell Transplants for AML

For subsequent stem cell transplants for AML, type of hematopoietic stem cell transplant (HSCT), and disease status at the time of HSCT will be summarized in frequency tabulations.

HSCT data will be presented in by-subject listings for subjects who receive HSCT.

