7.7.1.1.1. Determination of Event or Censoring for EFS

Evaluation of disease status, including evaluation of bone marrow and/or peripheral blood, is planned to be conducted at Screening (or as part of Pre-screening if within 28 days prior to randomization); Day 1 (± 7 days) of Weeks 9, 17, 25, 33, 41, 53, and every 24 weeks thereafter; at End of Treatment (EOT); during EFS follow-up on the same schedule; as clinically indicated; and/or any time that disease progression is suspected.

Determination of relapse date

Only disease assessments performed before the start date of subsequent anticancer therapies will be considered in the determination of relapse.

Confirmation is required for relapse. Assessments which are not done or not evaluable are ignored in the derivation of relapse confirmation. A subject will be considered to have relapsed if either of the following criteria are met:

- Relapse in 2 consecutive assessments that are at least 4 weeks apart
- Relapse with no further evaluable disease assessments before discontinuation from study or initiation of subsequent anticancer therapy

The date of relapse considered in the analyses will be the date when the first relapse, that is subsequently confirmed, is observed.

Determination of CR by 24 weeks

CR will be assessed until the date of relapse (that is subsequently confirmed). Only assessments performed on or before the start date of subsequent anticancer therapies will be considered in the determination of CR.

The protocol allows a 1-week window for disease assessments. Therefore, a subject will be considered to have achieved “CR by 24 weeks” if the date of first CR is within 25 weeks (24 weeks target+1 week window) after the date of randomization:

CR by 24 weeks if date of first CR–date of randomization $\leq 24 \times 7 + 7$.

Determination of two or more missing assessments

In the primary analysis of EFS, if a subject has an EFS event (relapse or death) after two or more missing disease assessments, the subject will be censored at the last adequate disease assessment documenting no relapse before the missing assessments. The followings are the rules for determining whether two or more disease assessments are missed.

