7.7.2. Key Secondary Endpoints

The key secondary efficacy endpoints are CR, OS, CR+CRh, and OR. CR, CR+CRh and OR will be assessed until the date of relapse (that is subsequently confirmed). Only assessments performed on or before the start date of subsequent anticancer therapies will be considered in the determination of these response endpoints.

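### A CR first documented after HSCT conditioning and transplant can count as CR by 24 weeks, because the SAP leaves the conditioning date out of its only therapy cut-off for response

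*SAP*

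**What the plan says.** SAP 6.3.6 takes the earliest date on or after randomization "captured in the Anticancer Therapy eCRF page will be used in the analyses as the start of subsequent anticancer therapy". It then makes one exception: if the entry is HSCT conditioning, "the corresponding date will not be used in the derivation of start of subsequent anticancer therapy". The section describes the date as serving censoring in the efficacy analyses.

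The date has a second use. For EFS responder status, SAP 7.7.1.1.1 states: "Only assessments performed on or before the start date of subsequent anticancer therapies will be considered in the determination of CR". The first CR must fall "within 25 weeks (24 weeks target+1 week window) after the date of randomization". For CR, CR+CRh and OR, SAP 7.7.2 repeats the cut-off: "Only assessments performed on or before the start date of subsequent anticancer therapies will be considered in the determination of these response endpoints". SAP 7.7.3 applies an equivalent cut-off to the additional secondary efficacy endpoints, including CR+CRi. None of these sections requires the subject to be on study treatment, and none refers to the transplant date.

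Transplants are reported apart from anticancer therapies: "HSCT data will be presented in by-subject listings for subjects who receive HSCT" (SAP 7.6.1, against 7.6.2 for anticancer therapies).

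Protocol 12.5.1 has a censoring rule only: "Event-free survival will be censored upon initiation of a new anticancer therapy should a new therapy be initiated prior to any EFS event". It does not define new anticancer therapy and does not mention conditioning or HSCT. The protocol does expect transplanted subjects in EFS follow-up, since "bone marrow samples are optional during EFS follow-up for post-transplant subjects" (Table 6, footnote 12; similarly 10.7).

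**The concern.** The response cut-off exists so that a remission obtained under some other treatment is not credited to the randomized regimen. Leaving out the conditioning date opens one route around it. Not censoring EFS at transplant after a CR already achieved is a defensible choice. Letting conditioning and donor engraftment supply the qualifying CR is a different matter, and SAP 6.3.6 gives no sign that this was intended.

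The stake is the primary endpoint. A subject without CR by 24 weeks is an event on the day of randomization; a subject with CR is an event only at relapse or death. One reclassification therefore moves a subject from the earliest possible event time to the responder part of the curve. The same CR enters the CR rate, the second test in the fixed sequence, and later the CR+CRh rate and ORR.

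No planned analysis would show the effect. Of the five EFS sensitivity analyses in SAP 7.7.1.2, the first changes which relapse and death dates are used, the second and fourth change the stratification, the third changes the analysis set on eligibility and dosing grounds, and the fifth moves the event time of failures. None changes who counts as a responder under this rule.

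**Working it through.** **Reading the rules together.** Take a subject in CRi at Week 17 who stops study treatment, has conditioning and HSCT at about Week 19, and meets all CR criteria on Day 1 of Week 25.

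1. Window: the limit is 24 × 7 + 7 = 175 days after randomization. Day 1 of Week 25 is about 24 × 7 = 168 days after, so the CR is in time.
2. Therapy cut-off: the only entry on the Anticancer Therapy page is conditioning, which is ignored. No cut-off date exists, so the assessment counts.
3. SAP Table 5: discontinuation before 24 weeks is a failure only without CR by 24 weeks. This subject has one and is a responder.
4. Comparison: had the subject started any other anticancer drug at Week 19, the Week 25 CR would not count. Table 5 has no censoring row for non-responders, so the subject would be a Day 1 failure.

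**Reproducing the design.** Inputs (protocol 12.12, SAP Table 3): 200 subjects 1:1, 173 events, 1-sided 0.025, CR by 24 weeks 20% vs 40%, responder median EFS 14.6 vs 19.2 months, accrual 3 per month for 10 months then 5, dropout 5%. Failures are tied events on Day 1, responders are exponential, and the test is an unstratified log-rank.

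- Critical HR: exp(−1.96 × 2/√173) = 0.742 (stated 0.742).
- Simulated power, 5,000 trials: 81.9% (stated 80%). Mean analysis time is 50.7 months (stated 52).

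**Effect of a few reclassified subjects.** The documents give no HSCT rate, so 0 to 3 subjects is an assumption. To sit at the decision boundary, the AG-120 CR rate is set to 32% with control at 20%, where power is about 50%. Repeated runs of the simulation give these ranges:

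| Extra responders | Probability of significance |
|---|---|
| none | 50 to 52% |
| 1 / 2 / 3 in AG-120 | 55 to 56% / 58 to 60% / 64 to 65% |
| 1 / 2 / 3 in control | 43 to 45% / 40% / 33 to 35% |
| 1 in each arm | 49% |

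Each AG-120 responder raises the mean log-rank Z by about 0.1: from 1.98 to 2.33 for three, and (2.33 − 1.98)/3 = 0.12. In probability this is about (64 − 50)/3 = 4.7 points each.

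**Effect as a rate.** Suppose a stated share of each arm (100 subjects, so 2% is 2 subjects and 5% is 5) has a first CR only after transplant. The table compares counting it as CR, as the SAP does, with counting it as failure.

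| Control / AG-120 | SAP rule | Counted as failure |
|---|---|---|
| Design alternative, 2% / 2% | 81% | 82% |
| Design alternative, 5% / 5% | 79% | 81% |
| Design alternative, 0% / 5% | 93% | 81% |
| Design alternative, 5% / 0% | 62% | 82% |
| No drug effect, 0% / 2% | 4.5% | 2.6% |
| No drug effect, 0% / 5% | 9.4% | 3.0% |
| No drug effect, 5% / 5% | 2.9% | 2.9% |

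In the rows with no drug effect, the drug changes neither CR nor EFS apart from the transplant-derived CRs, and Monte Carlo error is about 0.3 to 0.5 points. The 5% rows lie outside the 0 to 3 subjects assumed above and serve as an upper range.

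**The case against.** **The scenario is narrow.** Candidates for intensive chemotherapy are excluded, protocol 5.1 places transplantation within intensive treatment, and six cycles is the planned minimum. Transplant and full CR, including ANC, platelets and RBC-transfusion independence, must all fall within 175 days. Marrow sampling is optional after transplant, which makes a new CR less likely to be documented. All of this stands, and it is why the assumed number is 0 to 3, including zero.

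**The eCRF may close the gap.** Only the conditioning option is exempted. If the transplant itself, or an earlier non-conditioning therapy, is entered on the same page, that date applies. The documents do not say whether the transplant is entered there. This stands as a condition on the finding, and it is also a reason to write the rule down.

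**The protocol is not contradicted.** A reader might infer that the SAP breaks the protocol's rule on new anticancer therapy, or makes a major change that SAP Section 2 says needs an amendment. The documents do not support that. The protocol rule concerns censoring, its key term is undefined, and the protocol has no rule on which assessments count toward CR. Follow-up after transplant does not settle the matter either way, because the protocol's sensitivity analysis without censoring for subsequent therapy also needs such follow-up.

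**The direction is unknown.** A reader might infer that the rule favors AG-120 because a more active arm sends more subjects to transplant. No passage says so. The relevant subjects are those transplanted before any CR, and a drug that produces more CRs beforehand could leave fewer of them in its own arm.

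**The preferred handling is a choice of estimand.** Read literally, the protocol would censor the example subject when conditioning starts, not count a failure. That is true. But SAP Table 5 already makes a non-responder who starts any other therapy a Day 1 failure, so the proposal only gives conditioning the same treatment.

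**Conclusion.** The gap is real as a matter of text: the exemption in SAP 6.3.6 carries over into every response determination, and a post-transplant first CR within 175 days is then a qualifying CR. It is an unexplained exemption to an undefined term, out of step with the SAP's own exclusion of responses reached under other therapy. The SAP does not label such a CR as achieved on study treatment, and that reading should not be attributed to it.

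The likely size is small. Balanced between arms, the effect on EFS power is about 1 to 2 points. Unbalanced, each affected subject shifts the probability of significance near the boundary by roughly 4 to 5 points upward if in AG-120, and by a similar or slightly larger amount downward if in control. The inflated 1-sided rejection rates (4.5% and 9.4%) arise only if transplant-derived CRs fall in the AG-120 arm alone, which the documents give no reason to expect. The conclusion rests on the assumed 0 to 3 subjects, on no earlier non-conditioning entry, and on the transplant not being recorded on the Anticancer Therapy page. The change is still worth making because it is cheap and removes a question about who is a responder in the primary endpoint.

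**What to change.** - In SAP 6.3.6, limit the exemption to EFS censoring. In 7.7.1.1.1, 7.7.2 and 7.7.3, count toward CR by 24 weeks, CR, CR+CRh, OR and CR+CRi only assessments on or before the earlier of the start of subsequent anticancer therapy and the start of HSCT conditioning. EFS follow-up through transplant after a CR already reached is unchanged.
- Add one analysis to SAP 7.7.1.2 that treats conditioning as new anticancer therapy. Responders are censored at the last adequate assessment before it, and subjects without a prior CR stay Day 1 failures as Table 5 has it for other therapies.
- State in the protocol and SAP whether HSCT or its conditioning is new anticancer therapy, and in the SAP on which eCRF page the transplant date is recorded.

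Cost: a few sentences and one additional run. The conditioning date is already collected on the Anticancer Therapy page. The downside is possibly one or two fewer CRs. The wording should be settled before unblinding.
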